#### **5.2.8. Standard derivations and reporting conventions**

The following conversion factors will be used to convert days into weeks, months or years:  
1 week = 7 days, 1 month = 30.4375 days, 1 year = 365.25 days.

Demographics and physical measurements:

- Age [years]:
  - $(\text{date of given informed consent} - \text{date of birth} + 1) / 365.25$
  - In case of missing day, day only: Age [years]:  $(\text{year/month of given informed consent} - \text{year/month of birth})$
  - In case only year of birth is given: Age [years]:  $(\text{year of given informed consent} - \text{year of birth})$

The integer part of the calculated age will be used for reporting purposes.

- $\text{BMI (kg/m}^2\text{)} = \text{weight (kg)} / [\text{height (m)}]^2$
- $\text{BSA (m}^2\text{)} = ([\text{height (cm)} \times \text{weight (kg)}] / 3600)^{0.5}$

For reporting conventions, mean and median should generally be displayed one more decimal place than the raw data and standard deviation should be displayed to two more decimal places than the raw data. Percentages will be reported to one decimal place. The rounding will be performed to closest integer / first decimal using the common mid-point between the two consecutive values. Eg, 5.1 to 5.4 will be rounded to an integer of 5, and 5.5 to 5.9 will be rounded to an integer of 6.

### **5.2.9. Unscheduled visits**

Generally, data collected at unscheduled visits will be included and analyzed for both safety and efficacy analyses in the same fashion as the data collected at scheduled visits except where otherwise noted in the sections that follow. Descriptive statistics (mean, SD, median, minimum, maximum, quartiles) by nominal visit or time point for safety endpoints such as laboratory measurements, ECGs and vital signs will include only data from scheduled visits.

### **5.2.10. Adequate baseline tumor assessment**

Adequate baseline is defined using the following criteria:

- All baseline assessments must be within 31 days prior to and including the ‘start date’.
- All documented lesions must have non-missing assessments (ie, non-missing measurements for target lesions and non-missing lesions assessment status at baseline for non-target lesions).

### **5.2.11. Adequate post-baseline tumor assessment**

An adequate post-baseline assessment is defined as an assessment where a response of CR, PR, SD, non-CR/non-PD, or PD can be determined (see Section 6.2.2.1). Time points where the response is not evaluable (NE) or no assessment was performed will not be used for determining the censoring date.

## **5.3. Methods to Manage Missing Data**

### **5.3.1. Missing data**

Unless otherwise specified, all data will be evaluated as observed, and no imputation method for missing values will be used.

In all patient data listings imputed values will be presented. In all listings imputed information will be flagged.

Missing statistics, eg when they cannot be calculated, should be presented as ‘ND’ or ‘NA’. For example, if N=1, the measure of variability (SD) cannot be computed and should be presented as ‘ND’.

### **5.3.1.1. Pharmacokinetic concentrations**

#### **Concentrations Below the Limit of Quantification**

For all calculations, figures and estimation of individual pharmacokinetic parameters, all concentrations assayed as below the level of quantification (BLQ) will be set to zero. In log-linear plots these values will not be represented. The BLQ values will be excluded from calculations of geometric means and their CIs. A statement similar to ‘All values reported as BLQ have been replaced with zero’ should be included as a footnote to the appropriate tables and figures.

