- Pharmacokinetic parameters for axitinib will be listed and summarized by cycle and study day using descriptive statistics (n, mean, SD, %CV, median, minimum, maximum, geometric mean and its associated %CV, and 95% CI). For Tmax, the range (min, max) will also be provided. Only patients who have a matched pair of estimated axitinib PK parameters available on both planned treatments (when administered alone and in combination) will be included in the axitinib PK parameter summary tables. PK parameters with zero values will be excluded from the calculation of geometric means and its associated %CV. If an inpatient dose escalation or reduction occurs, dose-dependent PK parameters (AUC and Cmax) for that patient may be dose-normalized when it is known that the drug exhibits linear PK within the dose range and other PK parameters will be reported as estimated; or may only be included in descriptive statistics and summary plots up to the time of the dose change. In addition, dose-normalized axitinib Cmax and AUC parameters will be summarized (as described above) using data pooled across cohorts in which different axitinib doses were administered.
- Box plots for AUCτ and Cmax for axitinib (during treatments when given alone and in combination) will be generated. Individual data points, the geometric mean and the median of the parameter in each treatment will be overlaid on the box plots. If a cohort has limited evaluable PK data (n<4), matchstick plots showing changes in AUC and Cmax for each drug (during treatments when given alone and in combination) in individual patients will then be generated. The geometric mean of the parameter in each treatment will be overlaid in the plots. In addition, box plots for dose-normalized axitinib Cmax and AUCτ parameters will be created using data pooled across cohorts in which different axitinib doses were administered.
- Ctrough and Cmax for avelumab will be plotted for each treatment group using a box-whisker plot by cycle and day within cycle in order to assess the attainment of steady-state. Individual data points, the geometric mean and the median of the parameter in each treatment will be overlaid on the box plots.

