### PK parameters and immunogenicity status

The following analyses will include patients in both the immunogenicity analysis set and in the PK parameter analysis set. The PK endpoints pertinent to the immunogenicity analyses are  $C_{\text{trough}}$  and  $C_{\text{max}}$ .

Blood samples for avelumab PK will be collected as outlined in the “Schedule for Pharmacokinetic Sample Collection” table of the Schedule of Assessments section of the protocol.

$C_{\text{trough}}$  and  $C_{\text{max}}$  will be summarized descriptively (n, mean, SD, CV, median, minimum, maximum, geometric mean, its associated CV, and 95% CI) by nominal time and ADA status. Linear-linear and log-linear plots of mean and median for  $C_{\text{trough}}$  and  $C_{\text{max}}$  over nominal time and by ADA status will be presented.

Among patients with treatment-induced ADA, analyses will be conducted to assess whether  $C_{\text{trough}}$  and  $C_{\text{max}}$  have any changes before and after the first positive ADA assessment. To be included in this analysis, patients must have the same PK parameter available both before and after the first positive ADA assessment. Relative PK day will be calculated as:

$$(\text{PK assessment nominal day}) - (\text{first positive ADA assessment nominal day}).$$

Nominal day is the protocol scheduled timing for an assessment. For example, if  $C_{\text{trough}}$  is collected on Day 1 of Cycle 2 and the first positive ADA result is observed on Day 1 of Cycle 3, then the relative PK day for this  $C_{\text{trough}}$  is -14. Linear-linear and log-linear plots of mean and median for  $C_{\text{trough}}$  and  $C_{\text{max}}$  over relative PK day will be presented.

As data permit, the analyses described above will be repeated for nAb.

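### The geometric mean and 95% CI of avelumab Ctrough by ADA status leave out BLQ troughs, so they can understate an ADA effect on exposure, and no BLQ count is planned that would show it

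*SAP*

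**What the plan says.** SAP 5.3.1.1 gives three rules for BLQ concentrations.

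- For calculations, figures and derivation of individual parameters, the SAP directs that "all concentrations assayed as below the level of quantification (BLQ) will be set to zero".
- Log-linear displays leave such concentrations out.
- Geometric means get a rule of their own: "The BLQ values will be excluded from calculations of geometric means and their CIs".

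It also asks for a footnote on the relevant tables and figures saying that BLQ results were replaced by zero. No drug, visit or analysis is exempted.

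SAP Table 2 defines Ctrough as the predose concentration in multiple dosing, read directly from the data. A BLQ trough is therefore an observed Ctrough of zero, not a missing value. The 50% suppression rule in SAP 5.3.1 covers samples not done, not taken or flagged as anomalous. BLQ is not on that list.

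Under its PK heading, SAP 6.2.6.3 says that avelumab Ctrough and Cmax each "will be summarized descriptively (n, mean, SD, CV, median, minimum, maximum, geometric mean, its associated CV, and 95% CI) by nominal time and ADA status". It adds "Linear-linear and log-linear plots of mean and median for" both parameters, by ADA status. A further analysis looks before and after the first positive ADA result in patients with treatment-induced ADA. For that analysis "patients must have the same PK parameter available both before and after the first positive ADA assessment", and the display is again mean and median on both scales.

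**The concern.** One way ADA can lower exposure is by speeding up clearance, and a trough with no measurable drug is the strongest form of that signal. Dropping a value because it is low is selection on the outcome. If BLQ troughs are more frequent in ADA-positive patients, the geometric mean for that group rises and the contrast with ADA-negative patients shrinks.

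The geometric mean is the only statistic listed in SAP 6.2.6.3 with a CI beside it, so it is the one likely to be carried into a report. The section lists a single n. A reader could not see that the geometric mean rests on fewer values than the median next to it, and the footnote would say that BLQ had been replaced by zero, which is not what was done for the geometric mean.

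**Working it through.** The plan states no figure on this point, so there is none to reproduce. The check has two parts.

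**Direction (needs no assumed LLQ).** Every excluded value lies below every retained one. Removing them can only raise a group's geometric mean. The ratio of ADA-positive to ADA-negative moves toward 1 when BLQ is more frequent in the ADA-positive group and the retained values are of similar size.

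**Size (illustration only).** Let G be the geometric mean of the quantifiable troughs, f the share BLQ, and value each BLQ trough at LLQ/2. The geometric mean of all troughs is G^(1−f) × (LLQ/2)^f, so exclusion inflates it by (2G/LLQ)^f. The assumed LLQ of 10% or 1% of G gives 2G/LLQ = 20 or 200.

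| Share BLQ | LLQ = 10% of G | LLQ = 1% of G |
|---|---|---|
| 5% | 20^0.05 = 1.16 | 200^0.05 = 1.30 |
| 10% | 20^0.10 = 1.35 | 200^0.10 = 1.70 |
| 25% | 20^0.25 = 2.11 | 200^0.25 = 3.76 |

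The SAP expects at most about 55 patients, so an ADA-positive group may be small. If it held 8 (assumption), one BLQ trough is 12.5%, and the inflation is 20^0.125 = 1.45 to 200^0.125 = 1.94.

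Next, compare all the planned statistics. Assumptions: ADA-negative troughs log-normal with geometric mean 20 units and CV 60%; LLQ 0.2 or 1.0 units (1% or 5%); a share f of ADA-positive troughs BLQ and the rest unaffected. The ratios below are ADA-positive to ADA-negative, from 400,000 simulated values per group. They match the closed forms: 1 under exclusion, (LLQ/40)^f with LLQ/2, and 1 − f for the arithmetic mean.

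| Share BLQ | Geometric mean, BLQ excluded (SAP) | Geometric mean, LLQ/2 (LLQ 0.2 to 1.0) | Arithmetic mean, BLQ = 0 (SAP) | Median, BLQ = 0 (SAP) |
|---|---|---|---|---|
| 10% | 1.00 | 0.59 to 0.69 | 0.90 | 0.93 |
| 25% | 1.00 | 0.27 to 0.40 | 0.75 | 0.79 |
| 40% | 1.00 | 0.12 to 0.23 | 0.60 | about 0.59 |
| 60% | 1.00 | 0.04 to 0.11 | 0.40 | 0.00 |

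That is the extreme case. If ADA shifts the whole distribution, exclusion weakens the signal without erasing it. With a true geometric mean ratio of 0.10 and log-scale SD 1.2 in the ADA-positive group (assumptions), the SAP rule gives 0.11 with LLQ 0.2 (3% BLQ), 0.18 with LLQ 1.0 (28% BLQ) and 0.26 with LLQ 2.0 (50% BLQ). The median ratio stays at 0.10 in all three.

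**Is BLQ plausible?** Protocol 3.1 gives avelumab a half-life of 3 to 5 days. With simple exponential decay, 14 days leaves 2^(−14/3) = 3.9% to 2^(−14/5) = 14.4% of peak. If ADA halved the half-life (assumption), 2^(−14/1.5) = 0.16% to 2^(−14/2.5) = 2.1% would remain. Whether either range falls below the LLQ cannot be told from the documents.

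**The case against.** The strongest reply is that the rest of the table discloses the drop. BLQ stays as zero in the arithmetic mean, median and minimum, and in the linear plots. At 25% BLQ the planned mean and median ratios are 0.75 and 0.79. The exclusion is per value, so one BLQ trough does not take a patient out of the PK parameter set (SAP 4.3.2). SAP 6.2.6.3 also requires listings that combine immunogenicity and PK data. All of this stands, and it defeats one inference a reader might draw: that ADA-positive patients whose drug has been cleared are removed from the ADA comparison. They are not.

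The before-and-after analysis names no geometric mean. Only its log-linear version can be affected, and the SAP does not say whether BLQ values leave the plotted mean and median or are merely not drawn.

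Two other inferences also fail. The sentence "PK parameters with zero values will be excluded from the calculation of geometric means and its associated %CV" in SAP 6.2.3.1 belongs to the axitinib bullet; the operative rule for avelumab is in SAP 5.3.1.1. Nor is the comparison with earlier single-agent troughs shown to be biased. The plan names no statistic for it, the only single-agent trough statistic in Protocol 1.2.3 is a median, and the BLQ handling in those studies is not given.

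It is fair, too, that a geometric mean cannot contain a zero, so some convention is needed, and that LLQ/2 is itself arbitrary: at 10% BLQ the inflation moves from 1.35 to 1.70 only because the assumed LLQ changed. The analysis is descriptive, with no formal test (SAP 5.1.1), and Protocol 9.5.1.4 plans a separate population PK analysis of avelumab.

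None of this answers the narrower point. One reported estimate and its CI depend on the drug being quantifiable, in a comparison where loss of quantifiable drug is part of the effect sought. The PK and immunogenicity sections ask for no BLQ count that would reveal it.

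**Conclusion.** The point holds in a limited form. Under SAP 5.3.1.1 the geometric mean and 95% CI of on-treatment avelumab Ctrough by ADA status describe quantifiable troughs only. They can understate an ADA effect, and the prescribed footnote misdescribes them. The log-linear display shares the weakness. Cmax is sampled close to the end of infusion and is unlikely to be BLQ, so the issue is essentially about Ctrough.

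The upward direction within a group is certain whenever any on-treatment trough is BLQ. Attenuation of the ADA contrast further requires BLQ to be more frequent in ADA-positive patients. The size is unknown: every figure in the tables rests on an assumed LLQ and BLQ share, and if no trough is BLQ the effect is nil. This is an inexpensive improvement to a descriptive analysis. It does not invalidate the immunogenicity assessment.

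**What to change.** For avelumab samples taken after the first infusion, amend SAP 5.3.1.1 and 6.2.6.3 as follows.

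1. Print the number and percentage of BLQ values at each visit by ADA status, and the number of values behind each geometric mean.
2. Beside the geometric mean that excludes BLQ, report a geometric mean and 95% CI that keeps BLQ values, either at LLQ/2 or by left-censored log-normal maximum likelihood. Choose the method in advance and state the LLQ.
3. Say how BLQ values enter the mean and median on log-linear plots.
4. Reword the footnote so that it says BLQ was set to zero for the arithmetic statistics and was excluded, or handled by the stated method, for the geometric mean.

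Samples before the first infusion can keep the present rule.

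The cost is SAP wording and a small program change, with no new data. The downside is that LLQ/2 is a convention and the added estimate depends on it. The printed BLQ counts let a reader judge how much.

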#### **Deviations, Missing Concentrations and Anomalous Values**

In summary tables and plots of median profiles, concentrations will be set to missing if one of the following cases is true:

1. A concentration has been reported as ND (ie, not done) or NS (ie, no sample);
2. A deviation in sampling time is of sufficient concern or a concentration has been flagged as anomalous by the clinical pharmacologist.

Summary statistics will not be presented at a particular time point if more than 50% of the data are missing. For analysis of pharmacokinetic concentrations, no values will be imputed for missing data.

### **5.3.1.2. Pharmacokinetic parameters**

Whether actual or nominal PK sampling time will be used for the derivation of PK parameters will be determined by the results of interim PK analyses. If a PK parameter cannot be derived from a patient’s concentration data, the parameter will be coded as NC (ie, not calculated). NC values will not be generated beyond the day that a patient discontinues.

In summary tables, statistics will be calculated by setting NC values to missing. Statistics will not be presented for a particular treatment if more than 50% of the data are NC. For statistical analyses (ie, analysis of variance), PK parameters coded as NC will also be set to missing.

If an individual patient has a known biased estimate of a PK parameter (due for example to a deviation from the assigned dose level), this will be footnoted in summary tables and will not be included in the calculation of summary statistics or statistical analyses.

## **5.3.2. Handling of incomplete dates**

### **5.3.2.1. Disease history**

Incomplete dates for disease history (eg, initial diagnosis date, date of documented, locally advanced, inoperable or metastatic disease diagnosis, date of response or progression in prior treatment) will be imputed as follows:

- If the day is missing, it will be imputed to the 15th day of the month.

- If both day and month are missing and the year is prior to the year of the first study treatment, the month and day will be imputed as July 1st.
- If both day and month are missing and the year is same as the year of the first study treatment, the month and day will be imputed as January 1st.
- If the date is completely missing, no imputation will be performed.

#### **5.3.2.2. Adverse events**

Incomplete AE-related dates will be imputed as follows:

- If the AE onset date is missing completely, then the onset date will be replaced by the start of study treatment.
- If only the day part of the AE onset date is missing, but the month and year are equal to the start of study treatment, then the AE onset date will be replaced by the start of study treatment. For example, if the AE onset date is --/JAN/2015, and study treatment start date is 15/JAN/2015, then the imputed AE onset date will be 15/JAN/2015.
- If both the day and month of the AE onset date are missing but the onset year is equal to the start of study treatment, then the onset date will be replaced by the start of study treatment. For example, if AE onset date is --/--/2014, and study treatment start date is 19/NOV/2014, then the imputed AE onset date will be 19/NOV/2014.
- In all other cases the missing onset day or missing onset month will be replaced by 1.
- Incomplete stop date will be replaced by the last day of the month (if day is missing only), if not resulting in a date later than the date of patient's death. In the latter case the date of death will be used to impute the incomplete stop date.
- In all other cases the incomplete stop date will not be imputed. If stop date of AE is after the date of cut-off outcome of AE is ongoing at cut-off.

#### **5.3.2.3. Prior and concomitant medications**

Incomplete prior/concomitant medication dates will be imputed as follows:

- If the medication date is missing completely, then the medication date will be replaced by the start of study treatment.
- If the day of medication date is missing, but the month and year are equal to the start of study treatment, then the medication date will be replaced by the start of study treatment. For example, if the medication start date is --/JAN/2015, and study treatment start date is 15/JAN/2015, then the imputed medication start date will be 15/JAN/2015.
- If both the day and month of medication start date are missing but the start year is equal to the start of study treatment, then the medication date will be replaced by the start of study treatment. For example, if the medication start date is --/--/2014, and study

treatment start date is 19/NOV/2014, then the imputed medication start date will be 19/NOV/2014.

- In all other cases the missing medication day or missing medication month will be replaced by 1.
- Incomplete stop date will be replaced by the last day of the month (if day is missing only), if not resulting in a date later than the date of patient's death. In the latter case the date of death will be used to impute the incomplete stop date.
- In all other cases the incomplete medication stop date will not be imputed.

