5.7. Concomitant Treatments(s)

Medications or vaccinations specifically prohibited in the Exclusion Criteria ([Section 4.2](#)) are also not allowed during the active treatment period, except for administration of the inactivated influenza vaccine.

If there is a clinical indication for one of these or other medications or vaccinations specifically prohibited during the trial, discontinuation from study therapy or medication/vaccination may be required. The final decision on any supportive therapy or vaccination rests with the investigator and/or the patient's primary physician. However, the

decision to continue the patient on study therapy or medication/vaccination schedule requires the mutual agreement of the investigator, the sponsor, and the patient.

Concomitant treatment considered necessary for the patient's well being may be given at the discretion of the treating physician.

All concomitant treatments, blood products, as well as non-drug interventions received by patients from screening until the end of study visit will be recorded on the CRF.

Concomitant medications and treatments, including herbal supplements, will be recorded from 28 days prior to the start of study treatment and up to 90 days after the last dose of study treatment. All concomitant medications should be recorded in the CRF including supportive care drugs (eg, antiemetic treatment and prophylaxis), and the drugs used to treat adverse events or chronic diseases, and non-drug supportive interventions (eg, transfusions).

Concurrent anticancer therapy with agents other than avelumab and axitinib is not allowed. Medications intended solely for supportive care (ie, antiemetics, analgesics, megestrol acetate for anorexia) are allowed.

Recommended medications to treat infusion-related reactions, hypersensitivity reactions, flu-like symptoms, tumor lysis syndrome and immune-related events are reported in [Sections 5.3.5.5, 5.3.5.6, 5.3.5.7, and 5.3.5.8](#), respectively.

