#### 6.5.4. Concomitant medications and non-drug treatments

The following analyses will be based on the safety analysis set by treatment group.

**Concomitant medications** are medications, other than study medications, which started prior to first dose date of study treatment and continued on on-treatment period as well as those started during the on-treatment period. **Prior medications** are medications, other than study medications and pre-medications for study drug, which are started before the first dose of study treatment.

Prior and concomitant medications will be summarized from the 'General Concomitant Medications' eCRF page. Pre-medications for study drug will also be summarized separately from the 'Pre-Medication Treatment' eCRF page.

Summary of prior medications, summary of concomitant medications and summary of pre-medications will include the number and percentage of patients by Anatomical Therapeutic Chemical (ATC) Classification level 2 and preferred term. A patient will be counted only once within a given drug class and within a given drug name, even if he/she received the same medication at different times. If any prior or concomitant medication is classified into multiple ATC classes, the medication will be summarized separately under each of these ATC classes. The summary tables will be sorted on decreasing frequency of drug class and decreasing frequency of drug name in a given drug class. In case of equal frequency regarding drug class (respectively drug name), alphabetical order will be used. In case any specific medication does not have ATC classification level 2 coded term, it will be summarized under 'Unavailable ATC classification' category.

A listing of prior medications and a listing of concomitant medications will be created with the relevant information collected on the 'General Concomitant Medications' eCRF page. A listing of pre-medications will be created with the relevant information collected on the 'Pre-Medication Treatment' eCRF page.

All concurrent procedures, which were undertaken any time during the on-treatment period, will be listed according to the eCRF page 'General Non-drug Treatments'.

A listing of concurrent procedures will be created with the relevant information collected on the 'General Non-drug Treatments' eCRF page.

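### SAP 5.3.2.3 can impute a medication start that falls after the drug's own recorded stop, so a drug that ended before treatment is tabulated as concomitant instead of prior

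*SAP*

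**What the plan says.** SAP Section 5.3.2.3 completes medication start dates by four rules:

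- Date wholly missing: "If the medication date is missing completely, then the medication date will be replaced by the start of study treatment".
- Day alone unknown, with the known part matching first dose: "If the day of medication date is missing, but the month and year are equal to the start of study treatment"; the first-dose date is used.
- "If both the day and month of medication start date are missing but the start year is equal to the start of study treatment": the first-dose date is used.
- Everything else: "In all other cases the missing medication day or missing medication month will be replaced by 1".

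No start-date rule refers to the stop date. Stop dates have their own rule: a missing day becomes the last day of the month, limited by the date of death, and stop dates lacking more than the day are left as they are.

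Section 6.5.4 defines prior medications as those "which are started before the first dose of study treatment". Concomitant medications are those begun earlier and carried on into the on-treatment period, plus those begun within it. Section 5.2.7 opens that period at first dose. Under Protocol Section 5.7, medications "will be recorded from 28 days prior to the start of study treatment", so drugs taken and finished before treatment are in the data.

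Section 5.3.2.2 treats adverse event onset in the same way ("If the AE onset date is missing completely, then the onset date will be replaced by the start of study treatment"), with the same matching rules for partial dates.

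**The concern.** Using the first-dose date is a sensible default when nothing is known about timing. Here something is known: the recorded stop date shows that the drug ended before treatment began, and the rule overrides it. The result is a record that starts after it stops. It also lands in the wrong table, because a start on the first-dose day is not before first dose and is inside the on-treatment period. For these records the error always runs the same way: prior use is understated and concomitant use overstated.

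The SAP does use this kind of information elsewhere. Section 5.3.3.4 lets the end date of a new anti-cancer therapy limit its imputed start, and Section 5.3.2.3 itself checks imputed stop dates against death. The omission for medication starts looks like an oversight.

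**Working it through.** No sample size or power figure is involved. The check applies the stated rules to test records.

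**Step 1: reproduce the SAP's own examples.** --/JAN/2015 with first dose 15/JAN/2015 gives 15/JAN/2015. --/--/2014 with first dose 19/NOV/2014 gives 19/NOV/2014. Both agree with Section 5.3.2.3.

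**Step 2: classification, from Sections 6.5.4 and 5.2.7.**

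- Prior: imputed start < first dose.
- Concomitant: imputed start on or after first dose and within the on-treatment period, or imputed start < first dose with the drug ongoing or stopped on or after first dose.

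**Step 3: apply the rules as written.**

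| First dose | Start recorded | Stop recorded | Imputed start | Classified as | Correct? |
|---|---|---|---|---|---|
| 15/JAN/2015 | missing | 10/JAN/2015 | 15/JAN/2015 | concomitant only | no |
| 15/JAN/2015 | --/JAN/2015 | 10/JAN/2015 | 15/JAN/2015 | concomitant only | no |
| 19/NOV/2014 | --/--/2014 | 30/OCT/2014 | 19/NOV/2014 | concomitant only | no |
| 15/JAN/2015 | --/DEC/2014 | 10/JAN/2015 | 01/DEC/2014 | prior only | yes |
| 15/JAN/2015 | --/--/2009 | 10/JAN/2015 | 01/JAN/2009 | prior only | yes |
| 15/JAN/2015 | --/--/2009 | ongoing | 01/JAN/2009 | prior and concomitant | yes |
| 19/NOV/2014 | --/MAR/2014 | ongoing | 01/MAR/2014 | prior and concomitant | yes |
| 15/JAN/2015 | missing | ongoing | 15/JAN/2015 | concomitant only | true start unknown |
| 19/NOV/2014 | --/--/2014 | ongoing | 19/NOV/2014 | concomitant only | true start unknown |

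In the first two rows the imputed start falls 15 − 10 = 5 days after the stop. In the third row it falls 20 days after (1 day to 31 October, then 19).

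**Step 4: apply a cap.** If stop < first dose, set start = min(date from the existing rules, stop date). The first three rows become 10/JAN/2015, 10/JAN/2015 and 30/OCT/2014, and all three are prior only. The other six rows do not change. In particular, the cap leaves the last two rows out of the prior table, since they have no stop date to act on.

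**The case against.** The strongest reply is that imputing to first dose is deliberately cautious, that the tables concerned are descriptive in a study with no formal hypothesis testing, and that SAP Section 5.3.1 requires imputed values to be flagged in listings. All of that is true, and it keeps the point small. It does not defend the rule, because caution about unknown timing is no reason to contradict a recorded stop date, and flags in listings do not correct the summary counts.

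Two stronger inferences are tempting, and the reply defeats both.

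- **Treatment-emergent adverse events.** A reader might infer that these are inflated in the same way, since Section 5.3.2.2 has the same gap and serious events are reported from consent. Protocol Section 8.2, however, puts adverse events, serious or not, on the CRF only from first dose. Section 8.14.2 keeps the serious-event form separate from the AE CRF, and SAP Section 6.6.1 draws serious events from the AE eCRF page. Few events that ended before treatment should therefore be there to misclassify.
- **Antihypertensives.** A reader might infer that baseline use would look as though it began on axitinib. Section 6.5.4 puts continued and newly started drugs in one concomitant summary, and no planned table isolates new starts. An ongoing drug is counted there once, whatever its start date.

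Nor does the error reach the identification of immune-related events: Appendix 1 of the SAP links medications to events by AE identifier and ATC code, not by medication date.

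**Conclusion.** The point stands in a limited form. The rule misplaces a medication when its start is wholly missing, or partial and matching first dose, and its stop is known to precede first dose. It would be wrong to say that incomplete dates in general are affected: the last of the four rules keeps an earlier known month or year, and those drugs classify correctly.

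The size cannot be stated. The documents do not say how many medication dates are incomplete, and any patient count would rest on an assumed rate. The consequence is confined to the descriptive prior and concomitant tables; no effect on DLT or efficacy results is shown. Section 6.5.2.2 makes receipt of an excluded concomitant medication reportable, but the SAP does not say that imputed dates drive that identification, so no consequence can be claimed there.

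A separate matter should not be folded into this one. Ongoing drugs with no start date, or with a partial date matching first dose, are also missing from the prior table. A reader might blame the absent stop-date check. The cause is different: a start set to the first-dose day cannot satisfy a definition that requires it to be earlier. These drugs still appear as concomitant.

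**What to change.** In SAP Section 5.3.2.3, add: if the stop date, complete or imputed, is before first dose, take the start as the earlier of the stop date and the date given by the existing rules, and classify the medication as prior only. Because an imputed stop is the last day of its month, the cap acts only where the drug had ended before first dose even on the latest possible date. Stop dates lacking the month are not imputed, so the cap would not reach them.

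Add the same cap to Section 5.3.2.2, so that no event can have an onset after its end; the expected effect is close to nil.

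Optionally, and as its own decision, list ongoing medications as prior as well as concomitant when the start is wholly missing, or partial and matching first dose. Both cases need naming, since a rule for wholly missing starts alone would leave the matching partial dates out.

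The cap costs one sentence in each section and a minor program change, and it uses only dates already held. The optional step would also list as prior a few drugs that were truly started on treatment, so it is a matter of preference.
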